2.0	5-Jun-2017	
Amendment 1
 
Amendment rationale: to incorporate changes to the analysis plan due to protocol amendments and implement changes to align with Novartis guidelines and program standards
 
Main changes:
 
• Change document name to Statistical Analysis Plan (SAP) for alignment with updated process• Remove interim futility and efficacy analyses for PFS to reflect protocol amendments• Update analyses based on BIRC assessment of imaging data to reflect change to an audit-based assessment• [REDACTED]• Update definition of Safety Set to reflect the latest Novartis Oncology standard definition 
Specific other changes
 
• Clarified that Asian vs. non-Asian analyses are based on race, not ethnicity• Change “LEE011” to “ribociclib” in multiple places throughout the document 
Section 1
 
• Update introduction to refer to the protocol version the SAP is based on 
Section 2.1
 
• Update last contact date derivation details based on the latest SAP template and the data panels available in the study 
Section 2.3
 
• Update definition of per protocol set to include requirement of at least one dose and remove requirement of evaluable for efficacy• Update list of protocol deviations leading to exclusion from per protocol set• [REDACTED] 
Section 2.4
 
• Update section title to refer to therapies since it’s not limited to medications• Remove detailed list of prohibited medications and replace with reference to protocol• Expand on description of specific impact of concomitant therapies on analyses and clarify here and elsewhere that palliative radiation and continue of combination therapy alone after end of study treatment will not be considered as new antineoplastic therapies 
Section 2.5
 
• Clarify definition of PD too late as reason for unknown BOR• Update calculation of missing tumor assessments to align with Novartis RECIST macro• Remove detailed algorithm for waterfall plot construction

Version	Date	Changes
		Section 3.2
		
• Clarify use of IRT data versus CRF data for variables related to stratification factors• Include definitions for disease-free interval and endocrine sensitivity• Add clarification for biopsy to be considered separately from other prior antineoplastic surgeries• Add further details for summary of prior antineoplastic therapies
		Section 3.5
		
• Add summary in disposition table for number of patients entering survival follow-up
		Section 3.6
		
• Clarify last date of exposure to goserelin for patients who died or were lost to follow-up• Update dose intensity calculations to use duration of exposure to treatment component rather than duration of exposure to study treatment• Adjust DI calculation for goserelin to consider the dosing schedule (once every 28 days)• Remove calculation of RDI on a per-patient basis across treatment components• Add further details for definitions of dose interruption, delay and reduction• Add specific definitions of partial discontinuation of ribociclib/placebo and goserelin
		Section 3.7
		
• Separate concomitant and post-treatment therapies• Add summary for first and second new systemic antineoplastic medication after discontinuation of study treatment
		Section 3.8
		
• Clarify how the different sources of overall lesion response are used• Specify the primary analysis will be based on FAS including all data up to the cutoff date• Add table of censoring rules to section 3.8.1.1• Clarify that allocation of patients to NSAI/tamoxifen subgroups for supportive efficacy analyses are based on IRT stratification data• Increase the number of time points at which Kaplan-Meier estimates of survival probabilities are produced• Add details of audit-based BIRC assessment of PFS• Clarify details of multivariate Cox regression models for PFS and OS• Remove some of the minor supportive analyses for PFS, namely summary of difference in days to progression per local and central review, summary of missing tumor assessments, and time to first and second tumor assessment• • Clarify summary of time to response for responders is a descriptive summary• Clarify parts of the definition of time to definitive deterioration in ECOG PS

Version	Date	Changes
		
• For EQ-5D-5L PRO, change “index score” to “visual analog scale” for consistency with the protocol• Clarify the repeated measures analyses of PROs
		Section 3.9
		
• Clarify conventions for AE reporting• Update list of AE tables to be produced• Change “Clinically notable AEs” to “AEs of special interest” to match standard definition, and clarify/update description of these• Include some additional details regarding laboratory parameter and CTC grade derivations• Update list of liver function test criteria to be summarized and clarified that combined categories need not be concurrent• Include box plot of laboratory parameters• Add analyses of time to first occurrence of laboratory toxicities• Add description of analysis to be performed for urinalysis• Clarify how averaging of unscheduled ECGs is performed• Clarify notable ECG values to be summarized• Add analysis of time to grade 2 or worse QT prolongation• [REDACTED]
		Section 3.10
		
• [REDACTED]• [REDACTED]• Broaden definition of evaluable ribociclib/LEQ803 concentration to ribociclib doses of 200 mg, 400 mg, and 600 mg [REDACTED] ribociclib dose• [REDACTED]• [REDACTED]• Added linear model to summarize C_{trough}• [REDACTED]• [REDACTED]• Remove PK-ECG model and add graphical summaries of PK-ECG and PK-liver function• [REDACTED]• [REDACTED]
		Section 3.11
		
• [REDACTED]

Version	Date	Changes
		
Clarify details of analyses to be performed
		Section 3.13 
[REDACTED]
		Section 3.14 
Update interim analysis descriptions due to protocol amendments [REDACTED]
		Section 3.16 – 3.18 
Update sample size calculation to reflect changes in protocol amendments
		Section 4 
Update analysis descriptions for clarity and remove extraneous details and SAS code from analysis descriptionsClarified analysis for duration of follow-up
3.0	27-Sep-2017	Amendment 2 Amendment rationale: to clarify some analysis conventions and terminology used List of changes: 
Section 2.1.7: Clarify the definition of baseline as it relates to RECIST-based endpoints, to consider baseline valid if within seven days of treatment start date.Section 2.3.2: Remove one redundant sentence from the definition of the Safety set to avoid potential confusionSection 2.3: Include a section on withdrawal of informed consent to ensure data after withdrawal of consent are not included in analyses.Section 3.2.2:
Add number of metastatic sites summary to diagnosis and extent of cancer summarySimplify de novo/DFI definitionsChange endocrine resistant/sensitive terminology to more generic wordingSection 3.8.1.5:
Specify that NSAI/tamoxifen subgroup analyses will be based on assigned combination partner per CRF, for consistency with other subgroup analyses. The analysis according to IRT stratification factor are part of a separate analysis.Change endocrine resistant/sensitive terminology as described for Section 3.2.2Section 3.8.2.2: Change endocrine resistant/sensitive terminology as described for Section 3.2.2Section 3.11.6.2: Remove reference to “each time point” since only baseline data are included[REDACTED]

Version	Date	Changes
		
• Section 3.13: Delete bullet point indicating PFS [REDACTED] may be identical if adequate tumor assessments continue after initiation of next-line therapy, to avoid potential confusion [REDACTED]. Remove no baseline assessment as censoring reason.• [REDACTED]• Section 4.2.5:
• Increase the number of samples for bootstrap correlation estimate. Specify window for comparison of timing of response assessments.

Table of contents

Table of contents	7
List of tables	11
List of figures	11
1 Introduction	14
1.1 Study Design.....	14
1.2 Objectives	15
2 Definitions and general methodology	17
2.1 Definitions	17
2.1.1 Study drug and study treatment.....	17
2.1.2 Date of first administration of study drug.....	17
2.1.3 Date of last administration of study drug.....	17
2.1.4 Date of first administration of study treatment	17
2.1.5 Date of last administration of study treatment	18
2.1.6 Study day.....	18
2.1.7 Baseline	18
2.1.8 On-treatment assessment/event.....	19
2.1.9 Last contact date.....	19
2.2 Data included in the analysis	20

Table 3-3 Outcome and event/censor dates for PFS analysis.....	35
Table 3-4 ECOG Performance Scale.....	43
Table 3-5 Time windows for ECOG PS assessments.....	43
Table 3-6 Time windows for patient reported outcomes.....	44
Table 3-7 AEFI groupings	50
Table 3-8 Clinically notable ECG values	53
██████████	60
██████████	64
Table 3-11 Timelines for interim and final analyses.....	65
Table 4-1 Local versus central disease progression assessments	72

List of figures

Figure 1-1 Study design.....	15
------------------------------	----

List of abbreviations

AE	Adverse event
ATC	Anatomical Therapeutic Chemical
AUC	Area Under the Curve
BOR	Best overall response
CI	Confidence Interval
CBR	Clinical benefit rate
CR	Complete response
CRF	Case Report Form
CRO	Contract Research Organization
CRS	Case retrieval strategy
CSR	Clinical study report
CT	Computed tomography
CTCAE	Common Terminology Criteria for Adverse Events
CV	Coefficient of variation
Δ QTcF	Change from baseline in QTcF
DAR	Dosage administration Record
DI	Dose Intensity
DMC	Data Monitoring Committee
DOR	Duration of Response
ECG	Electrocardiogram
ECOG	Eastern Cooperative Oncology Group
EOT	End of treatment
FAS	Full analysis set
HER2	Human epidermal growth factor receptor 2
HR	Hazard Ratio
HRQoL	Health-Related Quality of Life
IRT	Interactive Response Technology
LFT	Liver Function Test
LLOQ	Lower Limit of Quantification
MedDRA	Medical Dictionary for Regulatory Activities
MRI	Magnetic resonance imaging
NCI	National Cancer Institute
NMQ	Novartis MedDRA queries
NSAI	Non-steroidal aromatase inhibitor
ORR	Overall response rate
OS	Overall survival
PAS	Pharmacokinetic analysis set
PD	Progressive disease

PDI	Planned dose intensity
PDS	Programming Datasets Specifications
PFS	Progression-free survival
PhRMA	Pharmaceutical Research and Manufacturers of America
PK	Pharmacokinetic
PPS	Per Protocol Set
PR	Partial response
PRO	Patient Reported Outcome
PS	Performance Status
PT	Preferred term
QTcF	QT interval corrected by Fridericia method
RAP	Report and Analysis Process
RDI	Relative dose intensity
RECIST	Response Evaluation Criteria In Solid Tumors
SAE	Serious adverse event
SAP	Statistical Analysis Plan
SD	Stable disease
SD	Standard deviation
SEC	Safety Event Categories
SMQ	Standardized MedDRA queries
SOC	System organ class
TA	Tumor assessment
TBIL	Total Bilirubin
TEAE	Treatment-emergent adverse event
TFLs	Tables, Figures, Listings
UNK	Unknown

1 Introduction

This document describes the detailed statistical methodology to be used for the Clinical Study Report (CSR) for the primary PFS analysis of study CLEE011E2301, a phase III, randomized, double-blind, placebo-controlled study of LEE011 (ribociclib) or placebo in combination with tamoxifen and goserelin or a non-steroidal aromatase inhibitor (NSAI) and goserelin for the treatment of premenopausal women with hormone receptor positive, HER2-negative, advanced breast cancer.

The content of this SAP is based on protocol amendment 4 (clee011e2301-v04--protocol). All decisions regarding final analysis, as defined in the SAP document, have been made prior to database lock and unblinding of the study data.

CSR deliverables (shells for tables, figures, listings) and further programming specifications are described in the Tables, Figures & Listings (TFL) shells and Programming Datasets Specifications (PDS), respectively.

1.1 Study Design

This is a phase III randomized, double-blind, placebo-controlled global study comparing the combination of tamoxifen or a NSAI (letrozole or anastrozole) + goserelin + LEE011 to tamoxifen or a NSAI (letrozole or anastrozole) + goserelin + placebo in premenopausal women with HR+, HER2-negative advanced breast cancer.

Approximately 660 patients will be randomly assigned to one of the below treatment arms in 1:1 ratio:

- a. [Tamoxifen or a NSAI (letrozole or anastrozole)] + goserelin + LEE011
- OR,
- b. [Tamoxifen or a NSAI (letrozole or anastrozole)] + goserelin + placebo.

Randomization will be stratified by the presence of liver and/or lung metastases (yes versus no), prior chemotherapy for advanced disease (yes versus no), and endocrine combination partner (tamoxifen and goserelin versus NSAI (letrozole or anastrozole) and goserelin).

Treatment with tamoxifen or NSAI in this study will be based on the patient's prior (neo) adjuvant therapy for breast cancer as outlined in the Clinical Study Protocol. The choice of NSAI (letrozole or anastrozole) is left to the discretion of the investigator. Once assigned, changing the dose or type of endocrine therapy is not permitted.

PFS, as assessed by the local radiologists/investigators and using RECIST 1.1 criteria will be the primary endpoint. PFS as assessed through audit-based blinded independent central review will be used for supportive evidence of the primary efficacy endpoint.

[figure not shown]
An independent Data Monitoring Committee (DMC) will monitor unblinded safety and PK data during the trial. Separate DMC RAP documents specify the analyses to be performed for the DMC reviews.

Overall survival is a key secondary endpoint in this study and will be analyzed provided the primary endpoint PFS is statistically significant. A Lan-DeMets alpha spending function with O'Brien Fleming type stopping boundary (as implemented in East 6.3) will be used to maintain

the overall type-I error rate for OS. The interim OS analyses will be performed by Novartis. Further details regarding the group sequential design are provided in [Section 3.14](#).

The study design is summarized in [Figure 1-1](#).

Figure 1-1 Study design

[figure not shown]
1.2 Objectives

[figure not shown]
The study objectives and corresponding endpoints as specified in the protocol are provided in [Table 1-1](#).

Table 1-1 Study objectives

Objective	Endpoint	Analysis
Primary		
To determine whether treatment with tamoxifen or a NSAI + goserelin + LEE011 prolongs PFS compared to treatment with tamoxifen or a NSAI + goserelin + placebo in premenopausal women with HR+, HER2-negative advanced breast cancer	PFS per local assessment and RECIST 1.1	Section 3.8.1
Key secondary		
To determine whether treatment with tamoxifen or a NSAI + goserelin + LEE011 prolongs OS compared to treatment with tamoxifen or a NSAI + goserelin + placebo in premenopausal women with HR+, HER2-negative advanced breast cancer.	OS	Section 3.8.2.1
Other secondary		

Objective	Endpoint	Analysis
To evaluate the safety and tolerability of LEE011 in combination with tamoxifen + goserelin or a NSAID + goserelin.	Frequency/ severity of adverse events, lab abnormalities	Section 3.9
To evaluate the two treatment arms with respect to response rate and clinical benefit rate (CBR).	ORR as defined by RECIST 1.1. CBR, defined as percentage of patients with CR, PR per RECIST 1.1 or SD lasting 24 weeks or longer	Section 3.8.2.2 and 3.8.2.3
To describe time to response (TTR) and duration of response (DOR) in each treatment arm.	Time to response and duration of response per RECIST 1.1	Section 3.8.2.4 and 3.8.2.5
To evaluate the two treatment arms with respect to time to deterioration of ECOG PS.	Time to definitive deterioration of the ECOG PS from baseline	Section 3.8.2.6
To evaluate patient reported outcomes for health-related quality of life in the two treatment arms.	Time to 10% deterioration in the global health status/QOL scale score of the EORTC QLQ-C30 Change from baseline in the global health status/QOL scale score of the EORTC QLQ-C30	Section 3.8.2.7

2 Definitions and general methodology

2.1 Definitions

2.1.1 Study drug and study treatment

Study drug is defined as ribociclib or matching placebo.

Study treatment is defined as ribociclib + (tamoxifen or a NSAID) + goserelin, or matching placebo + (tamoxifen or a NSAID) + goserelin.

2.1.2 Date of first administration of study drug

The date of first administration of study drug is defined as the first date when a nonzero dose of study drug is administered and recorded on the dose administration DAR CRF. The date of first administration of study drug will also be referred to as start of study drug. Similar definitions apply for the other components of study treatment.

2.1.3 Date of last administration of study drug

The date of last administration of study drug is defined as the last date when a nonzero dose of study drug is administered and recorded on the DAR CRF date. Similar definitions apply for the other components of study treatment.

2.1.4 Date of first administration of study treatment

The date of first administration of study treatment is defined as the first date when a nonzero dose of any component of study treatment is administered and recorded on the DAR CRF. The

date of first administration of study treatment will also be referred to as the start of study treatment.

2.1.5 Date of last administration of study treatment

The date of last administration of study treatment is defined as the last date when a nonzero dose of any component of study treatment was administered and recorded on the DAR CRF.

2.1.6 Study day

The study day will be calculated as:

- The date of the event (visit date, onset date of an event, assessment date etc.) – reference start date + 1 if event is on or after the reference start date;
- The date of the event (visit date, onset date of an event, assessment date etc.) – reference start date if event precedes the reference start date.

The reference start date for safety assessments (e.g. adverse event onset, laboratory abnormality occurrence, vital sign measurement, dose interruption etc.) is the start of study treatment. (Note: if an adverse event starts before the start of study treatment the study day displayed on the listing will be negative).

The reference start date for all other, non-safety assessments (i.e., tumor assessment, death, disease progression, tumor response, ECOG performance status, and patient reported outcomes (PRO)) is the date of randomization. In other words, all efficacy time-to-event variables (e.g. progression-free survival, overall survival, time to response) will be calculated from date of randomization. (Example: if randomization date is 15DEC2014, start of study drug is on 18DEC2014, and the date of death is 28DEC2014 then the study day when the death occurred is 14).

The study day will be displayed in data listings.

2.1.7 Baseline

For efficacy evaluations, the last available assessment on or before the date of randomization will be used as the “baseline” value or “baseline” assessment. In the context of baseline definition, the efficacy evaluations also include ECOG performance status and patient-reported outcomes. For RECIST-based endpoints (e.g. PFS, best overall response), a window of 7 days after the start of study treatment will be allowed, i.e. the baseline will also be considered valid if it occurs within 7 days of the treatment start date.

For safety evaluations (e.g. laboratory assessments and ECG), the last available assessment before or at date of start of study treatment will be used as the ‘baseline’ assessment. Assessments specified to be collected post-dose on the first date of treatment are not considered as baseline values.

If patients have no value as defined above, the baseline results will be considered missing.

2.1.8 On-treatment assessment/event

Safety summaries and selected summaries of deaths will summarize only on-treatment assessments/events. An on-treatment assessment/event is defined as any assessment/event in the following time interval:

[date of first administration of study treatment, date of last administration of study treatment + 30 days], i.e. including the lower and upper limits. (Note: However, the calculation of study treatment duration will use different rules as specified in [Section 3.6.1](#)).

An AE started in the screening phase and ongoing in the on-treatment phase will not be considered an on-treatment AE unless it has worsened.

If the last date of study treatment is missing, any assessment/event occurring after the start of study treatment will be considered as on-treatment.

Data listings will include all assessments/events, flagging those which are not on-treatment.

Note: The date of first administration of study treatment and the date of last administration of study treatment are defined in [Sections 2.1.4](#) and [2.1.5](#), respectively.

2.1.9 Last contact date

For patients not known to have died at the analysis cut-off the last contact date will be derived using the last complete date among the following:

Table 2-1 Last contact date data sources

Source data	Conditions
Date of Randomization	No Condition
Last date patient was known to be alive from Survival Follow-up page	Patient status is reported to be alive, lost to follow-up or unknown.
Start/End dates from further antineoplastic therapy	Non-missing medication/procedure term.
Start/End dates from drug administration record	Non-missing dose. Doses of 0 are allowed.
Date of discontinuation/study phase completion from end of treatment or end of post-treatment follow-up disposition page	No condition.
Date of ECG assessment	At least one non-missing parameter value
Date of PRO assessment	At least one non-missing answer to questionnaire
Tumor (RECIST) assessment date	For non-target lesion: non-missing lesion status For target lesion: non-missing lesion diameter For new lesion: "Is there a new lesion?" = yes
Laboratory collection dates	At least one non-missing parameter value
	
Vital signs date	At least one non-missing parameter value

Source data	Conditions
Performance Status date	Non-missing performance status
Start/End dates of AE	Non-missing verbatim term
Concomitant medication date	Non-missing medication
████████████████████	██
Body fluid/Tissue Collection/Results	Non-missing result (positive/negative tumor cells)
██	██
Cardiac imaging date	Non-missing LVEF or overall interpretation

The last contact date is defined as the latest complete date from the above list on or before the data cut-off date. The cut-off date will not be used for last contact date, unless the patient was seen or contacted on that date. No date post cut-off date will be used. Completely imputed dates (e.g. the analysis cut-off date programmatically imputed to replace the missing end date of a dose administration record) will not be used to derive the last contact date. For patients who died, the last contact date is defined as the date of death. Partial date imputation is allowed for event (death)/censoring from the ‘Survival information’ eCRF.

The last contact date will be used for censoring of patients in the analysis of overall survival.

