### **7.1.6.4 Lost to follow-up**

For patients whose status is unclear because they fail to appear for study visits without stating an intention to withdraw consent, the investigator should show "due diligence" by contacting the patient, family or family physician as agreed in the informed consent and by documenting in the source documents steps taken to contact the patient, e.g. dates of telephone calls, registered letters, etc. A patient should not be considered lost to follow-up until due diligence has been completed. Patients lost to follow-up should be recorded as such on the appropriate Disposition CRF.

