### 10.5.1 Key secondary objective(s)

The key secondary objective of the study is to determine whether treatment with tamoxifen or a NSAI + goserelin + LEE011 prolongs OS compared to treatment with tamoxifen or a NSAI + goserelin + placebo.

OS is defined as the time from date of randomization to date of death due to any cause. If a patient is not known to have died, then OS will be censored at the date of last known date patient alive.

Assuming proportional hazards model for OS, the following statistical hypothesis for OS will be tested using a stratified log-rank test (stratified according to randomization stratification factors) at the one-sided 2.5% level of significance:

$$H_{02}: \theta_2 \geq 0 \text{ vs. } H_{a2}: \theta_2 < 0$$

where  $\theta_2$  is the log-hazard ratio (tamoxifen or a NSAI+goserelin+LEE011 arm vs. tamoxifen or a NSAI+goserelin+placebo arm) of OS.

The analyses for OS will be based on the FAS. The distribution of OS will be compared between the two treatment groups using a stratified log-rank test at one-sided 2.5% level of significance.

The final OS analysis will not be performed at the time point of the primary PFS analysis, but after additional follow-up. Therefore, a three-look design is considered for OS.

OS will be hierarchically tested in the following way:

1. The first potential time point for OS analysis will be at the time of the primary PFS analysis, when 123 deaths are expected. If PFS is statistically significant at this stage, OS will also be tested.
2. If OS is not statistically significant at this stage, the 2nd OS analysis will be planned after approximately 189 deaths.

3. If OS is not statistically significant at this stage, a final analysis is planned after approximately 252 deaths have been recorded.
4. If PFS is not statistically significant at the primary analysis, then OS will not be tested.

The type I error probability for OS tests will be controlled by using a Lan-DeMets (O'Brien-Fleming) alpha spending function at the one-sided type I error of  $\alpha=0.025$ . This guarantees the protection of the overall level  $\alpha = 2.5\%$  across the two hypotheses and the repeated testing of the OS hypotheses in the interim and the final analyses (Glimm 2010).

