## End dates

The end dates which are used to calculate ‘time to event’ variables are defined as follows:

- Date of death (during treatment as recorded on the treatment completion page or during follow-up as recorded on the study evaluation completion page or the survival follow-up page).
- Date of progression is the first assessment date at which the overall lesion response was recorded as progressive disease.

If applicable, if patients who discontinued due to ‘Disease progression’ are considered to be PD solely based on clinical deterioration, then add the following text in the protocol:

When there is no documentation of radiologic evidence of progression, and the patient discontinued for ‘Disease progression’ due to documented clinical deterioration of disease, the date of discontinuation is used as date of progression.

- Date of last adequate tumor assessment is the date the last tumor assessment with overall lesion response of CR, PR or SD which was made before an event or a censoring reason occurred. In this case the last tumor evaluation date at that assessment is used. If no post-baseline assessments are available (before an event or a censoring reason occurred) the date of randomization/start of treatment is used.
- Date of next scheduled assessment is the date of the last adequate tumor assessment plus the protocol specified time interval for assessments. This date may be used if back-dating is considered when the event occurred beyond the acceptable time window for the next tumor assessment as per protocol (see [Section 3.2.10](#)).

**Example** (if protocol defined schedule of assessments is 3 months): tumor assessments at baseline - 3 months - 6 months - missing - missing - PD. Date of next scheduled assessment would then correspond to 9 months.

- Date of discontinuation is the date of the end of treatment visit.
- Date of last contact is defined as the last date the patient was known to be alive. This corresponds to the latest date for either the visit date, lab sample date or tumor assessment date. If available, the last known date patient alive from the survival follow-up page is

used. If no survival follow-up is available, the date of discontinuation is used as last contact date.

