2.3.5 Patient classification

Patients may be excluded from the analysis sets defined above based on the protocol deviations entered in the database and/or on specific subject classification rules as defined in [Table 2-2](#).

Table 2-2 Patient classification based on protocol deviations and non-protocol deviation criteria

Analysis set	Protocol deviations leading to exclusion	Non-protocol deviation criteria leading to exclusion
FAS	No written informed consent	NA
Safety set	No written informed consent	No dose of study treatment

Per Protocol set	Any major protocol deviation as listed in definition of per protocol set	No dose of study treatment
------------------	--	----------------------------

Withdrawal of informed consent

Any data collected in the clinical database after a patient withdraws informed consent from all further participation in the trial, will not be included in the analysis. The date on which a patient withdraws full consent is recorded in the eCRF.

Death events may be used in the analysis if captured from public records (registers), local law and patient informed consent permitting.

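### Two SAP rules for overall survival (OS) can depart from censoring at the last date known alive: the unconditioned disposition-page date, and register deaths counted after consent withdrawal without register survival

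*SAP*

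**What the plan says.** Protocol 10.5.1 sets the OS rule: "If a patient is not known to have died, then OS will be censored at the date of last known date patient alive". Protocol Appendix 3, section 3.2.8, also defines last contact as a date on which the patient was known to be alive. It gives an order: the survival-page date is used if available, and "If no survival follow-up is available, the date of discontinuation is used as last contact date". The same list equates the date of discontinuation with the end-of-treatment visit.

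SAP (primary analysis) 2.1.9 implements OS censoring through Table 2-1: "The last contact date will be used for censoring of patients in the analysis of overall survival". The choice among sources is by recency: "The last contact date is defined as the latest complete date from the above list on or before the data cut-off date". One source is the "Last date patient was known to be alive from Survival Follow-up page", which does require known-alive status. Another is the "Date of discontinuation/study phase completion from end of treatment or end of post-treatment follow-up disposition page", whose condition column imposes nothing. The final SAP splits that row in two and again attaches no condition to either part.

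For lost patients, protocol 7.1.6.4 asks for documented attempts at contact and then says: "Patients lost to follow-up should be recorded as such on the appropriate Disposition CRF".

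For patients who withdraw consent, SAP (primary analysis) 2.3.5 excludes later data and then adds: "Death events may be used in the analysis if captured from public records (registers), local law and patient informed consent permitting". The corresponding paragraph of the final SAP (2.3.4) does not contain that sentence.

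**The concern.** Censoring at a date on which nobody knew the patient to be alive adds person-time during which a death could not have been seen. That lowers the estimated hazard in the arm concerned. It would also shorten the gap to cut-off behind the 98-day loss-to-follow-up label in SAP 3.8.2.1, so some lost patients would not be labelled as lost.

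The register provision works in the opposite direction. A withdrawn patient found dead contributes an event. One not found dead is censored at or before withdrawal, although the same search might have shown her alive. Censoring then depends on the outcome, and the hazard is raised.

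Both effects largely cancel in the hazard ratio if loss and withdrawal are equal between arms, and do not cancel if they differ. OS is the key secondary endpoint.

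**Working it through.** **1. The plan's own figures.** Inputs from protocol 10.7.2 and 10.9.1: HR 0.70, one-sided 2.5%, 252 deaths, looks at 123, 189 and 252.

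- Fixed design: 4 × (1.960 + 0.842)² / (ln 0.70)² = 247 deaths.
- Three-look Lan-DeMets (O'Brien-Fleming): bounds 3.003, 2.357 and 2.014; cumulative power 15.3%, 54.1% and 80.1%. The plan states 15%, 54% and 80%.

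These reproduce, and none depends on the censoring rule.

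**2. The texts side by side.**

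| Question | Protocol 10.5.1 and Appendix 3 | SAP Table 2-1 |
|---|---|---|
| Must the patient be known alive? | Yes | Yes for the survival page; no condition on disposition dates |
| Which date wins? | Survival page first | Latest complete date |
| Role of end-of-treatment date | Fallback if no survival follow-up; a visit date | Always eligible |
| Role of post-treatment disposition date | Not named as a source | Always eligible |

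No section found says what date the post-treatment disposition page holds for a lost patient who had no visit.

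**3. Size, by assumption.** From the documents: control median 33 months and HR 0.70, so λ = ln 2/33 = 0.0210 per month for placebo and 0.0147 for ribociclib; OS cut-off at month 40; 672 randomized. Assumed: exponential OS; uniform accrual over 660/33 = 20 months, so potential follow-up a is uniform on 20 to 40 months; loss or withdrawal hazard w = −ln(1 − p)/30, with p the proportion by 30 months (p = 5%, 10%, 15% give w = 0.0017, 0.0035, 0.0054). The HR is the ratio of deaths per person-time. Before either rule applies, with integrals over u from 0 to a and everything averaged over a:

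- deaths D = [λ/(λ + w)] × [1 − exp(−(λ + w)a)]; person-time Y = D/λ.

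*Disposition date d months after true last contact:* added time ΔY = ∫ w exp(−(λ + w)u) min(d, a − u) du; rate = D/(Y + ΔY).

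| Lost: placebo / ribociclib | HR, d = 1 | HR, d = 3 | HR, d = 6 |
|---|---|---|---|
| 5% / 5% | 0.700 | 0.700 | 0.700 |
| 10% / 10% | 0.700 | 0.700 | 0.700 |
| 10% / 5% | 0.701 | 0.704 | 0.707 |
| 5% / 10% | 0.699 | 0.696 | 0.693 |

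The shift favours the arm with more loss. With equal loss of 5 to 10%, the control median rises by about 0.06 to 0.65 months.

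*Register deaths with coverage r:* ΔD = r ∫ w exp(−(λ + w)u)[1 − exp(−λ(a − u))] du, and ΔY = r ∫ w exp(−(λ + w)u){[1 − exp(−λ(a − u))]/λ − (a − u)exp(−λ(a − u))} du; rate = (D + ΔD)/(Y + ΔY).

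| Withdrawn: placebo / ribociclib | HR, r = 50% | HR, r = 100% |
|---|---|---|
| 5% / 5% | 0.701 | 0.702 |
| 10% / 10% | 0.702 | 0.703 |
| 10% / 5% | 0.694 | 0.688 |
| 5% / 10% | 0.708 | 0.717 |
| 15% / 5% | 0.687 | 0.675 |
| 5% / 15% | 0.717 | 0.733 |

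The shift goes against the arm with more withdrawal. With equal withdrawal of 5 to 10%, about 3 to 13 deaths are added per 672 patients and the control median falls by 0.3 to 1.2 months. If register survivors are also followed to the search date, the added time becomes ΔD/λ, the rate returns to λ and the bias vanishes.

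Simulation with 2 million patients per scenario gives the same shifts to within about 0.001.

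**The case against.** The strongest reply on the disposition date is that no text shows it to be administrative. Protocol 7.1.5 ties the end-of-phase page to the date and reason for stopping treatment, and Appendix 3 treats discontinuation as a visit. Protocol 7.1.7 places the post-treatment page before survival follow-up, so a patient lost later would normally have a later survival-page date. Where no survival page exists, Appendix 3 also uses the end-of-treatment date. This stands in part. It narrows the exposure and makes the lag an assumption. It does not cover the post-treatment page, for which loss to follow-up is a listed reason and no date is defined.

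On registers, the wording is permissive and subject to law and consent, and some Table 2-1 rows are redacted. That also stands: the asymmetry is what the visible text produces if the permission is used.

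On size, the standard error of the log HR at 252 deaths is about 2/√252 = 0.126. A move from 0.700 to 0.688 is 0.017 on the log scale, or 0.14 standard errors. Patients and investigators were blinded until Amendment 6, which makes large imbalance less likely but does not rule it out. SAP 3.8.2.1 and 4.4 list OS censoring reasons and tabulate the gap from censoring to cut-off. That would help show unequal follow-up, though a late disposition date would itself shorten the gap.

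A reader might infer that the OS rules in general do not require a patient to be known alive. The documents do not support this. The protocol requires it, the survival-page row requires it, most other visible rows need a recorded value, and the cut-off date is barred unless the patient was seen or contacted that day. A reader might also infer that register survival is expressly excluded. It is simply not mentioned.

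**Conclusion.** The point holds as a departure of two SAP rules from the protocol's own definition. The disposition date enters without a contact requirement and can outrank a known-alive date, conditional on what the CRF collects. Register use after withdrawal, if exercised, counts events only.

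The effect on the HR is negligible with balanced rates (at most about 0.003). It reaches about 0.007 for the disposition date at 10% vs 5% lost with a six-month lag. For registers at full coverage it is about 0.012 at 10% placebo vs 5% ribociclib withdrawal (0.017 with the arms reversed) and up to about 0.033 at 15% vs 5%. Every rate, lag and coverage here is assumed: the only loss figure in the plan is the 10% for PFS in protocol 10.8. The number of deaths and the power stand.

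The documents do not support going further and calling the reported OS result biased. They show no imbalance in loss or withdrawal, and no evidence that register deaths were used.

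**What to change.** In Table 2-1, accept a disposition-page date only if the patient was seen or contacted on that date, or drop the row when the reason is loss to follow-up. In SAP 2.3.5, censor withdrawn patients at withdrawal in the main OS analysis and add register deaths in a sensitivity analysis. Alternatively, where law and consent permit, count the register search date as an alive date for those not found dead.

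The cost is a few lines of text, slightly fewer deaths or slightly shorter follow-up, and one extra sensitivity analysis. The alive-date option also needs the search date recorded. It may need permission as well, because protocol 7.1.8 treats withdrawal as ending collection of personal data.

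OS was already met at the second interim, so the change applies to a sensitivity analysis of that result and to any later descriptive OS update.
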